## 5 Administrative Details

Limited to participants in the ITT analysis set.

### 5.1 Participant Enrollment

#### Figure: Enrollment over time

- NHLBI enrollment figure

#### Table: Enrollment by site and sex

- Including details of all participants enrolled at substudy site

## 5.2 Participant Study and Treatment Disposition

Table: Participant status

	Total (N=XX)	Treatment Group	
		Pitavastatin (N=XX)	Placebo (N=XX)
Enrolled	XX (xx%)	XX (xx%)	XX(xx%)
Completed 24 mo follow-up	XX (xx%)	XX (xx%)	XX(xx%)
Timing of final visit (months from enrollment)) Median (P10-P90)			
Min-Max			
Did not complete substudy	XX (xx%)	XX (xx%)	XX(xx%)
Reason for Discontinuation Reasons from A5333S RP0002	XX	XX	XX
....	XX	XX	XX
Timing of discontinuation Before 4 month visit*	XX (xx%)	XX (xx%)	XX(xx%)
Between 4 and 24 month visits	XX (xx%)	XX (xx%)	XX(xx%)

Figure: Time to substudy discontinuation

- KM plot by treatment group

Table: Treatment disposition

		Total (N=XX)	Treatment Group	
			Pitavastatin (N=XX)	Placebo (N=XX)
Days to start of study treatment*	N	XX	XX	XX
	Median (P10-P90)	XX (XX-XX)	XX (XX-XX)	XX (XX-XX)
	Min-Max	0-X,XXX	0-X,XXX	0-X,XXX
	# missing	XX	XX	XX
	0-2	XX (XX%)	XX (XX%)	XX (XX%)
	3-14	XX (XX%)	XX (XX%)	XX (XX%)
	>14	XX (XX%)	XX (XX%)	XX (XX%)
	Will never start	XX (XX%)	XX (XX%)	XX (XX%)
Timing of treatment discontinuation	Before 4 month visit*	XX (XX%)	XX (XX%)	XX (XX%)
	Between 4 and 24 month visits	XX (XX%)	XX (XX%)	XX (XX%)
	On or after the 24 month visit	XX (XX%)	XX (XX%)	XX (XX%)
Reasons for discontinuation	Reasons from A5332 RP0003	XX (XX%)	XX (XX%)	XX (XX%)
	...	XX (XX%)	XX (XX%)	XX (XX%)

\* Includes participants who never started treatment

Figure: Time to treatment discontinuation

- KM plot by treatment group

## 5.3 CT Scan Availability

Table: CT scan availability

Table denominator is the ITT analysis set; table will be repeated in the per protocol analysis set.

		Total (N=XX)	Treatment Group	
			Pitavastatin (N=XX)	Placebo (N=XX)
Evaluable Entry CT scan	Qualitative read	XX (XX%)	XX (XX%)	XX (XX%)
	Quantitative read	XX (XX%)	XX (XX%)	XX (XX%)
	Paired reads	XX (XX%)	XX (XX%)	XX (XX%)
No Entry CT scan	scan	XX (XX%)	XX (XX%)	XX (XX%)

		Treatment Group		
		Total (N=XX)	Pitavastatin (N=XX)	Placebo (N=XX)
Reason no entry CT scan	Out of window	XX	XX	XX
	Missed visit	XX	XX	XX
	<other reasons>	XX	XX	XX
	Image quality	XX	XX	XX
Evaluatable Year 2 CT scan	Paired reads	XX (XX%)	XX (XX%)	XX (XX%)
	Qualitative read	XX (XX%)	XX (XX%)	XX (XX%)
	Quantitative read	XX (XX%)	XX (XX%)	XX (XX%)
No Year 2 CT scan		XX (XX%)	XX (XX%)	XX (XX%)
Reason no scan	Out of window	XX	XX	XX
	Premature discontinuation	XX	XX	XX
	Missed visit	XX	XX	XX
	<other reasons>	XX	XX	XX
	Image quality	XX	XX	XX
Evaluatable paired scans	Qualitative read	XX (XX%)	XX (XX%)	XX (XX%)
	Quantitative read	XX (XX%)	XX (XX%)	XX (XX%)
	Paired reads	XX (XX%)	XX (XX%)	XX (XX%)

Possible <Other reasons> based on the scan tracking form might include: Refusal, Unable to place IV or other technical issue, Renal insufficiency, Contrast allergy, BMI >40.

#### 5.4 Consort

See Appendix II for draft Consort based on scan reads. This will be expanded on to incorporate details of treatment status and analysis windows.

- Registered
  - Did not complete A5332 entry visit
- Within the ITT sample and by treatment group, Cross-tabulation of
  - Scan availability by treatment status
    - Baseline CTA completed (in versus outside of window)
    - Diagnostics baseline CTA
    - Completed follow-up CTA (in versus outside of window)
    - Diagnostic baseline and follow-up CTA
  - Treatment status
    - Completed treatment
    - Did not start treatment
    - Early treatment discontinuation

#### 5.5 Biomarker Availability

Table: Data availability Like the table below but scaled down out of window visits/samples.

Visit	[Visit windows]		Subjects Expected	of Expected Subjects		Total Biomarkers	
				Observed Visits	Biomarkers available	for day	for day & Baseline
Entry	TD-180	TD+1	XX	XX (XX%)	XX (XX%)	XX	
Entry +	TD+2d	TD+59d	XX	XX [XX%]	XX [XX%]		
Month 4-	TD-60d	TD-30d	XX	XX [XX%]	XX [XX%]		
Month 4	TD±30d		XX	XX (XX%)	XX (XX%)	XX	XX
Month 4+	TD+30d	TD+60d	XX	XX [XX%]	XX [XX%]		
Month 12			XX	XX	XX		
Month 24-	TD-180d	TD-30d	XX	XX [XX%]	XX [XX%]		
Month 24	TD±30d		XX	XX (XX%)	XX (XX%)		
Month 24+	TD+30d	TD+360d	XX	XX [XX%]	XX [XX%]		

Visit	[Visit windows]	of Expected Subjects		Total Biomarkers	
		Subjects Expected	Observed Visits	Biomarkers available	for day for day & Baseline
Month 36+		XX	XX	XX	
TD - Target date					

## 6 Participant Characteristics and Other Risk Factors

See *JAMA Open Table 1. Statistics by treatment group as described will be given in the study report; the summaries will likely be streamlined for the manuscript.*

The following defined at study entry only unless stated otherwise. The table denominator would be the ITT sample. A second table of the same information will be included for those with paired scans.

- Demographic and Behavioral characteristics
  - Age (years): Mean (SD) and percent by group (40-49; 50-59; 60+)
  - Sex: Percent women
  - Gender identity: Percent by group (Cisgender, Transgender spectrum, Not reported)
  - Race: Percent by group (White, Black or African American, Asian, Other)
  - Ethnicity: Percent by group (Hispanic or Latino, Not Hispanic or Latino, Unknown)
  - Other substance use (cocaine, heroin, methamphetamine)
- ASCVD Risk Score at REPRIEVE Entry
  - ASCVD risk score (%): Median (Q1, Q3) and percent by group (<2.5, 2.5-<5, 5-<10, 10+)
  - Smoking status: Percent by group (Current, Former, Never)
  - Use of antihypertensive medication: Percent yes
  - Systolic BP of those not on antihypertensive medication: Median (Q1-Q3) (P10, P90)
  - Total cholesterol (mg/dL) : Median (Q1-Q3) (P10, P90)
  - HDL-C (mg/dL) : Median (Q1-Q3) (P10, P90)
  - LDL calculated (mg/dL) : Median (Q1-Q3) (P10, P90)
  - Triglycerides (mg/dL) : Median (Q1-Q3) (P10, P90)
  - Family history of premature CVD: Percent yes
- Other Cardiovascular / metabolic characteristics at REPRIEVE Entry
  - BMI: (kg/m^2) Mean (SD) and percent by group (<24.9, 25-29.9, 30+)
  - Prior statin use: Percent yes
    - Based on site report at entry
  - Diabetes: Percent yes
  - Use of anti-diabetic therapy: Percent yes
  - Use of ACE/ARBs: Percent yes
  - Use of anti-platelets/anticoagulants: Percent yes
  - Use of non-statin lipid lowering agents Percent yes
- Cardiovascular / metabolic characteristics at Year 2
  - BMI: (kg/m^2) Mean (SD) and percent by group (<24.9, 25-29.9, 30+)
  - Prior statin use: Percent yes
    - Based on site report at entry
  - Diabetes: Percent yes
  - Use of anti-diabetic therapy: Percent yes; percent adding medication after baseline
  - Use of ACE/ARBs: Percent yes; percent adding medication after baseline
  - Use of anti-platelets/anticoagulants: Percent yes; percent adding medication after baseline
  - Use of non-statin lipid lowering agents Percent yes; percent adding medication after baseline
- HIV-related health history (all based on site report at entry)
  - Time since HIV diagnosis (years): Median (Q1, Q3) (P10, P90)
  - Nadir CD4 count (cells/mm^3): Percent by group (<50, 50-199, 200-349, ≥350, Unknown)
  - Total ART use duration (years): Percent by group (<5, 5-10, >10, Unknown)
  - Thymidine exposure: Percent yes
  - Abacavir exposure: Percent yes
  - TDF exposure: Percent yes
  - Protease inhibitor exposure: Percent yes

- HIV-related health at REPRIEVE entry
  - CD4 count (cells/mm3): Mean (SD)
  - HIV-1 RNA (copies/ml): Percent by group (<LLQ, LLQ-400, >400)
  - ART regimen: Percent by group (NRTI+INSTI, NRTI+NNRTI, NRTI+PI, NRTI-sparing, Other NRTI containing)
  - Entry NRTI: Percent by group (No NRTI, TDF, TAF, Abacavir, Other)
  - Entry INSTI: Percent by group (No INSTI, DTG, EVG, BIC, RAL)
- HIV-related health at Year 2
  - Most recent CD4 count (cells/mm3): Mean (SD)
  - Most recent HIV-1 RNA (copies/ml): Percent by group (<LLQ, LLQ-400, >400)
  - Change in class of ART from baseline: Percent yes
  - Current ART regimen: Percent by group (NRTI+INSTI, NRTI+NNRTI, NRTI+PI, NRTI-sparing, Other NRTI containing)
  - Change in NRTI from entry: Percent yes.
  - Current NRTI: Percent by group (TDF, TAF, Abacavir, No NRTI, Other)
  - Change in INSTI from entry: Percent yes.
  - Current INSTI: Percent by group (No INSTI, DTG, EVG, BIC, RAL)

## 7 Analysis Plan

### 7.1 General analysis Considerations

Outcome distributions will be described with median, Q1, Q3, P10, P90, minimum, and maximum and shown graphically. All primary treatment group comparisons will be performed ITT using a 5% type error. For continuous outcomes, inference will be based on differences in means adjusted for baseline and presented with two-sided, 95% confidence intervals.

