Failure to start statin : Included per randomized treatment (treatment policy) Change in statin strategy : Included per randomized treatment (treatment policy) Includes discontinuation or change of statin Evidence of critical stenosis at treatment start : Included per randomized strategy (treatment strategy) Interval stent placement or bypass *: Included per randomized strategy (treatment policy strategy) Death prior to Year 2 scan : Treated as missing data (hypothetical policy)	Missing data due to missed visits or unreadable scans will be assumed missing completely at random and ignored i.e., the primary analysis will be a complete case analysis including participants with pair baseline and year 2 scans. Sensitivity analyses will include multiple imputation for missing data.
Population-level summary measure	Analysis approach
Mean change NCP volume over 2 years	Linear regression (normal errors assumption). In the event of extreme violation of normality, outcomes will be log transformed (giving a percentage change interpretation of the treatment effect). Modeling will adjust for CD4 and sex (stratification factors), and for baseline NCP volume.

\* Stented or bypassed coronary artery segments are not considered on the entry and year 2 scan as part of the read protocol for plaque volume.

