##### 3.2.1 Change NCP volume over 2 years (Primary)

- Continuous outcome:
  - Absolute change: NCP volume at 2 years – NCP volume at entry
  - Percentage change: (NCP volume at 2 years – NCP volume at entry) / NCP volume at entry (Supportive)
- Based on quantitative read whenever available (including for participants with no evidence of NCP based on the corresponding qualitative read).
  - Participants without a quantitative read and no evidence of NCP based on the corresponding qualitative read will be assigned a value of zero for both absolute and percentage change.

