##### 3.2.2 Progression of NCP over 2 years (Primary)

- Binary outcome (Yes, No)
- Based on both quantitative and qualitative reads
  - Among participants without evidence of NCP at entry on the qualitative read, evidence of NCP at 2 years.
  - Among participants with evidence of NCP at entry on qualitative read, >0% increase in NCP volume
  - Participants with discordant outcomes based on qualitative and quantitative reads, progression will be defined by the quantitative read.

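### The A5333s SAP names two primary outcomes and tests each at 5% with no decision rule; if success on either counts, the chance of a false primary finding is about 9%

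*SAP*

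**What the plan says.** SAP 3.2 carries two headings marked primary: "Change NCP volume over 2 years (Primary" and "Progression of NCP over 2 years (Primary". Both also appear as outcome measures of the primary estimand in SAP 2.1. The only population-level summary measure given there is "Mean change NCP volume over 2 years".

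SAP 7.1 sets the error rate: "All primary treatment group comparisons will be performed ITT using a 5% type error". Continuous outcomes are to be "presented with two-sided, 95% confidence intervals".

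SAP 7.2 then describes three NCP comparisons:
- a baseline-adjusted regression of the change in volume among participants with plaque at entry;
- a stratified chi-squared test of incident NCP among those without it at entry;
- a stratified chi-squared test of progression in the whole substudy population.

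In SAP Appendix I, Table 9.2-1 describes its bold cells as the main targeted comparisons. Those cells are percent change (12% vs 5%) and incident NCP (21% vs 8%). SAP 3.2.1 nevertheless calls percent change supportive, and SAP 3.2 does not list incident NCP as a separate primary outcome.

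Protocol 9.6.1 recognises multiplicity, mentions the mechanistic hypothesis by name, and puts the overall level at 0.05. Its remedy is cautious reading of the supporting analyses and a look for consistency across endpoints. Neither the SAP nor protocol Appendix II gives an order, an alpha split, an adjustment or a both-must-succeed rule.

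**The concern.** Two tests, each at 5%, give two chances of a false positive. Without a rule, a result that is significant on one outcome and null on the other could be reported as a positive primary result, whichever of the two it is. The caution in protocol 9.6.1 covers supporting analyses, so it does not reach two outcomes that both carry the primary label. What is at stake is how much weight a split result can bear. This substudy explains mechanism and does not decide the main trial.

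**Working it through.** **Inputs (SAP Appendix I).** There are 800 participants, about 1:1, with 15% not evaluable: 800 × 0.85 = 680, or 340 per arm. Half have NCP at entry, so 170 per arm with and 170 without. The SD of percent change is 20%. Baseline volume is gamma with mean 250 and SD 200. Incident NCP over two years is 21% on control.

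**The plan's own power figures first.**
- Percent change: SE = 20 × √(2/170) = 2.169. For the stated 6% difference, 6/2.169 − 1.960 = 0.806, so power is 79.0%, not the stated 90%. For the table's 12% vs 5%, 7/2.169 − 1.960 = 1.267, so power is 89.7%.
- Incident NCP, 21% vs 8%: 92.9% power with 170 per arm. With continuity correction, 168 per arm are needed for 90%. This agrees with the plan.

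The 6% mismatch does not affect the error-rate question.

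**Error rate for either outcome.**
- Independent tests: 1 − 0.95² = 9.75%.
- The tests are positively correlated, because progression is largely the sign of the volume change ("Among participants with evidence of NCP at entry on qualitative read, >0% increase in NCP volume"). Bivariate normal results: correlation 0.4 gives 9.3%, 0.5 gives 9.1%, 0.7 gives 8.4%, 0.8 gives 7.8%.
- The documents give no correlation, so it was obtained by simulation: 8,000 null trials with control-arm distributions in both arms. The assumptions added were four equally likely sex-by-CD4 strata and a normal or right-skewed percent change. The tests were regression adjusted for baseline and strata, and a Mantel-Haenszel test. Each test alone rejected in about 5% of trials.

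| Volume tested in | Correlation | Either outcome significant |
|---|---|---|
| those with plaque at entry | about 0.37 | 9.2% to 9.6% |
| everyone | about 0.47 | 9.1% to 9.3% |

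Monte Carlo error is about 0.3 points.

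**False benefit only.** The ceiling is 1 − 0.975² = 4.94%. Simulation gives about 4.8%, against 2.5% for a single test.

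**Power under Table 9.2-1 (for costing the fix).**
- Volume, plaque at entry, change 30 (SD 68) vs 12 (SD 64): SE = √((68² + 64²)/170) = 7.16; 18/7.16 − 1.96 = 0.55; power about 71%.
- Volume, everyone, 19 (SD 51) vs 7 (SD 45): SE = √((51² + 45²)/340) = 3.69; 12/3.69 − 1.96 = 1.29; power about 90%.
- Progression with normal percent change: control 0.5 × Φ(12/20) + 0.5 × 0.21 = 46.8%; statin 0.5 × Φ(5/20) + 0.5 × 0.08 = 33.9%; power with 340 per arm about 93%. The plan's rounded 14-point difference gives about 96%.
- Progression confirmed only if volume also succeeds: with positive correlation this lies between the product of the two powers and the smaller of them. That is 66% to 71% (plaque at entry) or 84% to 90% (everyone). Simulation puts it at about 68% and 86%.

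**Holm.** If both nulls hold and the tests are independent, the error is 1 − 0.975² = 4.94%, and it never exceeds 5%. The simulated power loss is about 1 to 3 points per outcome, because the other outcome has usually passed. Plain Bonferroni would cost more: for the 7-point percent change, power falls from 89.7% to 83.8%.

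**The case against.** **Section 7.1 can be read per comparison.** On that reading each test does have a 5% error, and the SAP itself promises no more. This stands as a reading of 7.1. The overall 0.05 comes from protocol 9.6.1, and two unordered 5% tests do not deliver it.

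**The 9% needs an either-counts rule.** If both outcomes had to succeed, there would be no inflation. That is correct. The documents state neither rule, which is the gap.

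**The estimand table already points to mean change.** It gives one summary measure, and progression is mostly the sign of the same quantity. This is a fair guide to the intended lead outcome. But the same table lists progression beside it and 3.2.2 still calls it primary, so the conflict needs resolving.

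**Stronger readings that a reader might infer, and that the documents do not support:**
- *That there is a 9% chance of falsely claiming benefit.* The 9% counts false findings in either direction, whereas the primary hypothesis in SAP 1.2.1 is of reduced progression.
- *That there are three primary tests and an error of about 13%.* This adds the incident-NCP comparison. Table 9.2-1 treats it as a targeted comparison, but SAP 3.2 does not label it primary. It shows a need to reconcile the labels and does not establish a third primary test.
- *That a fixed order is free.* It costs the first outcome nothing, but it can cost progression a good deal (see the power figures above).

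**Conclusion.** The gap is real and of moderate size. With two outcomes labelled primary, each at 5%, and no decision rule, the two-sided chance of at least one false primary finding is about 9%. A false claim of benefit has a chance of about 4.8%, against 2.5% for one test. The figure rests on three things: success on either outcome being enough, the SAP's planning assumptions, and a correlation derived by simulation. Correlations from 0.3 to 0.8 move it only from 9.5% to 7.8%, so correlation between the outcomes does not bring it back to 5%. The documents do not show that the plan intended either outcome to suffice; they leave the question open.

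**What to change.** **Preferred.** In SAP 7.1, state that the error across the two primary outcomes is held at two-sided 5% by Holm: the smaller p-value is judged at 2.5% and, if it passes, the other at 5%. Familywise error is then about 4.9%, at a cost of about 1 to 3 points of power per outcome.

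**Alternative.** Follow the summary measure in SAP 2.1: make mean change in NCP volume the single primary outcome, and test progression at 5% only if volume succeeds. The chance of confirming progression then falls from about 93% to about 86% with volume tested in all paired scans, or to about 68% with volume tested only in those with plaque at entry. The label in 3.2.2 and the estimand table must change to match.

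**Under either choice:**
- State in 7.2 whether the primary volume test uses the estimand's paired-scan population or only those with plaque at entry. Do not simply call every subgroup comparison in 7.2 supportive, because the only volume regression described there is one of them.
- Reconcile the labels in 3.2 with Table 9.2-1 by saying whether the incident-NCP and percent-change comparisons are supportive.
- SAP version 1.0 was finalised on Mar 20, 2023. If treatment comparisons have since been seen, record the rule as a dated later clarification. Holm is easier to defend then, because it does not require choosing an order after the fact.

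The cost is a sentence in 7.1 and short edits to 7.2, plus 3.2.2 and the estimand table if the single-primary route is taken. No new data are needed.

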### 7.2 Statin effects on coronary plaque morphology

Outcome measures: See Sections 3.2 and 3.3

#### Table: Primary and secondary plaque outcomes

Among participants with plaque at entry, descriptive statistics for the change and percentage change in NCP volume over 2 years will be provided by treatment group with group comparisons made with linear regression with adjustment for baseline plaque volume and stratified by sex and CD4.

Among those without NCP at entry, the prevalence of incident NCP over 2 years will be compared with stratified chi-squared test.

To assess the mechanistic study population as a whole, the probability of NCP and total plaque progression over two years (see Section 3.2.2) will be compared by treatment group using a stratified chi-squared test.

The statin effect on high risk plaque features (any), including low attenuation and positive remodeling, will be assessed by comparing differences in the 2-year prevalence of high risk plaque morphology features between treatment groups using chi-squared (or Fisher's exact) tests as appropriate; these analyses will be performed overall and by subgroups defined by the presence of NCP at study entry.

*Sample table from Testosterone study, JAMA 2017*

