## 2 Objectives and Estimands

### 2.1 Primary Objective

To determine the effects of pitavastatin on the morphology and composition of coronary atherosclerotic plaque, (including the progression of noncalcified plaque (NCP) volume), and whether these effects are modulated by markers of inflammation and immune activation.

Primary Estimand	
Estimand description	An estimand defines the target of estimation for a particular trial objective (i.e. “what is to be estimated”). This combines all the estimand elements outlined below into a single, succinct sentence.
Treatment	Treatment groups
Pitavastatin 4mg per day	Pitavastatin 4mg per day or placebo
Target population	Analysis set
PWH on stable ART with low to moderate cardiovascular risk and no known current indication for statin treatment.	All randomized participants with a REPRIEVE (A5332) entry visit. Participants who were consented but never returned to the clinic for their REPRIEVE (A5332) entry visit (regardless of whether the participant was formally randomized) will be considered inadvertent enrollments and excluded.
Variable(s)	Outcome measure(s)
Change in noncalcified plaque volume (NCP)  Change in volume of plaque and calcified plaque will be examined as secondary variables.	See Section 3 for more detailed outcome descriptions • Absolute change in NCP volume from entry to year 2. • NCP progression defined as any increase (>0) in NCP volume or incident NCP for those without NCP at entry (based on qualitative read) For sensitivity analyses, • Qualitative assessment of at least one segment with NCP on the 2 year CT. • Quantitative NCP volume at 2 year CT
Handling of intercurrent events	Handling of missing data

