3.2.4 NCP volume at 2 years (supportive)

- Continuous outcome
- Based on quantitative read whenever available (including for participants with no evidence of NCP on the corresponding qualitative read).
  - Participants without a quantitative read and no evidence of NCP on the corresponding qualitative read will be assigned a value of zero.
- Outcome is defined regardless of availability of an entry scan

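### For absolute NCP change, one of two primary outcomes, SAP 2.1 analyses all ITT participants with paired scans, but the main comparison in SAP 7.2 is written for participants with plaque at entry

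*SAP*

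**What the plan says.** SAP 2.1 sets out the primary estimand. The analysis set is "All randomized participants with a REPRIEVE (A5332) entry visit". The first outcome is absolute NCP change from entry to year 2, modelled by linear regression adjusted for sex, CD4 count and baseline NCP volume. The one further restriction is the missing-data rule, under which "the primary analysis will be a complete case analysis including participants with pair baseline and year 2 scans".

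Three other sections agree with that population. SAP 3.2.1 keeps participants without visible NCP in the outcome: it is "Based on quantitative read whenever available (including for participants with no evidence of NCP based on the corresponding qualitative read"), and participants who also lack a quantitative read, with "no evidence of NCP based on the corresponding qualitative read will be assigned a value of zero for both absolute and percentage change", stay in. SAP 4.1 limits analyses of change by paired scans and by nothing else. SAP 7.1 makes all primary comparisons ITT.

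SAP 7.2, under its table of primary and secondary plaque outcomes, reads differently. "Among participants with plaque at entry, descriptive statistics for the change and percentage change in NCP volume over 2 years" are presented by arm and compared by baseline-adjusted linear regression. Participants without NCP at entry get a test of incident NCP. The full group appears in the sentence beginning "To assess the mechanistic study population as a whole, the probability of NCP and total plaque progression over two years", which is a stratified chi-squared test.

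If normality is badly violated, SAP 2.1 adds that "outcomes will be log transformed (giving a percentage change interpretation of the treatment effect"). SAP 3.2.4 says of year-2 volume: "Participants without a quantitative read and no evidence of NCP on the corresponding qualitative read will be assigned a value of zero".

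**The concern.** Two analysts working from the same SAP could report different primary results for absolute NCP change. One would follow 2.1 and estimate the effect in everyone with paired scans. The other would follow 7.2 and estimate it only in those with plaque at entry. These are different quantities in different people, and near the planned 50% entry prevalence they also differ in power. A choice between them made after the data are seen weakens the pre-specification of that outcome.

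The log fallback raises a smaller problem of the same kind. If it were triggered in the whole cohort, someone would have to decide afterwards how to handle values that have no logarithm.

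**Working it through.** **Source of the mismatch.** Protocol Appendix II, section 9.5.1, planned analyses by presence of NCP at entry unless otherwise noted, and 9.5.2 compared NCP change among those with plaque by a stratified t-test. SAP 7.2 keeps that structure and replaces the t-test with regression. SAP 2.1 and 3.2.1 moved to a whole-cohort absolute change.

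**Inputs.** From SAP Appendix I: 800 participants, equal allocation, 15% not evaluable, 50% with NCP at entry. Evaluable per arm: 800 × 0.85 / 2 = 340; with plaque at entry: 340 × 0.5 = 170. Inference is two-sided at 5% (SAP 7.1). I read plaque at entry as NCP at entry, as Table 9.2-1 does.

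**The plan's own figure.** The SAP states 90% power for a 6-point difference in percent change among those with plaque, SD 20. Power = Φ(Δ / (SD × √(2/n)) − 1.96). With n = 170, the standard error is 20 × √(2/170) = 2.169.
- Δ = 6: Φ(2.766 − 1.96) = 0.790.
- Δ = 7 (the table's 12% against 5%): Φ(3.227 − 1.96) = 0.897.

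The table's figures reproduce the stated power; the rounded 6 points does not. That is a separate matter. No design power is stated for absolute change.

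**Absolute change in the two populations.** Power = Φ(Δ / √((SD₁² + SD₂²)/n) − 1.96), with means and SDs from Table 9.2-1.

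| Population | Control | Statin | Difference | n per arm | Power |
|---|---|---|---|---|---|
| All paired (2.1) | 19 (51) | 7 (45) | 12 mm³ | 340 | Φ(12/3.689 − 1.96) = 0.902 |
| Plaque at entry (7.2) | 30 (68) | 12 (64) | 18 mm³ | 170 | Φ(18/7.162 − 1.96) = 0.710 |

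Consistency check: the NCP-free difference is 9 − 2 = 7 mm³, and 0.5 × 18 + 0.5 × 7 = 12.5, which agrees with 12 after rounding.

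**Baseline-adjusted simulation.** 3,000 runs, 340 per arm. From Appendix I: gamma entry volume, mean 250, SD 200; percent change with mean 12 or 5 and SD 20 (normality assumed); incident NCP 21% or 8%, with mean volume 40 or 20 and SD 20. Change is regressed on arm and baseline; sex and CD4 are left out because the documents give no effects for them. Prevalences of 75% and 90% are assumptions.

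| Entry prevalence | Whole cohort: effect, power | Plaque at entry: effect, power | Same verdict |
|---|---|---|---|
| 50% (planned) | −12.2 mm³, 0.927 | −17.5 mm³, 0.718 | 79.2% |
| 75% | −15.0 mm³, 0.939 | −17.7 mm³, 0.879 | 94.0% |
| 90% | −16.5 mm³, 0.944 | −17.6 mm³, 0.922 | 97.8% |

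Power with HC3 robust standard errors agrees within 0.005.

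**Log fallback.** At 50% prevalence, 53% of control and 66% of statin participants have a change of zero or less, so the change itself cannot be logged. Logged volumes fail at any assigned zero, and adding a constant c is one way round this. The table takes the extreme case in which every NCP-free scan is exactly zero; the constants are assumptions. The model is log((V₂+c)/(V₀+c)) on arm and log(V₀+c). Entries are effect (rejection rate).

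| Prevalence | c = 0.1 | c = 1 | c = 10 mm³ |
|---|---|---|---|
| 50% | −36.9% (0.991) | −26.5% (0.997) | −14.4% (1.00) |
| 75% | −22.9% (0.942) | −16.9% (0.985) | −10.2% (0.999) |
| 90% | −13.5% (0.862) | −10.8% (0.964) | −7.8% (0.997) |

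If a quarter of NCP-free participants are exact zeros and the rest read 1 to 20 mm³ (assumed; 1,000 runs, 50% prevalence), the effects are −20.3%, −16.8% and −11.0%, with rejection 0.883, 0.923 and 0.987. Restricted to non-zero volumes at both scans, the log-ratio effect is −6.5% at each prevalence.

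**The case against.** The strongest reply is that the estimand governs. SAP 2.1 names the population, outcome, summary measure and model, three other sections agree with it, and the 7.2 sentence is inherited protocol wording. Most of that stands: the whole cohort is the better reading. But 7.2 sits in the analysis plan under a heading for primary outcomes, does not call its regression supportive, and uses the group for which Appendix I states power on NCP volume. Its wording still needs aligning.

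A reader might go further in four ways that the documents do not support.
- That the SAP plans no whole-cohort analysis of NCP change. SAP 2.1 specifies one, and 7.2 also plans a table of effect modification on NCP change with no plaque restriction. That table names no model, so it does not settle the population.
- That both primary outcomes are affected. NCP progression is also primary (SAP 2.1 and 3.2.2), and 7.2 tests it in the population as a whole.
- That the supportive percentage change breaks down at a zero entry volume. SAP 7.2 confines that comparison to participants with plaque at entry, which largely deals with it.
- That the handling of zeros could decide the trial result. The fallback may never be used, the number of exact zeros is unknown because quantitative reads are used whenever available, and rejection stays at 86% or more in every case tabulated.

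It is also fair that 12 and 18 mm³ are different estimands. The power gap is the cost of adopting the 7.2 population, not a fault in 2.1.

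**Conclusion.** The conflict is real and should be fixed. It concerns one of two primary outcomes and is a disagreement between sections, not a missing analysis. On the plan's own table the choice moves the target difference from 12 to 18 mm³ and power from about 90% to about 71%. The significance verdict differs in about 21% of simulated runs at the planned 50% entry prevalence, falling to about 6% and 2% at an assumed 75% and 90%, so the practical effect depends on how common NCP at entry proves to be.

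The log fallback is secondary. It cannot be run as written on zero or negative changes or on assigned zeros. If triggered, the treatment of zeros would mainly alter the reported effect size, not the test result. Simulated residual excess kurtosis of 15.5 in the whole cohort and 7.0 in the plaque group makes the trigger plausible but not certain, and the SAP sets no threshold for it. Confidence is high on the mismatch and lower on how much the fallback would matter.

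**What to change.** In SAP 7.2, state that absolute NCP change is compared in all ITT participants with paired scans, as 2.1 specifies, and label the plaque-at-entry regression supportive.

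In SAP 2.1, replace the log fallback with the baseline-adjusted mean difference already adopted in 7.1, using robust or bootstrap standard errors. If a log-ratio analysis is kept, limit it to participants with non-zero volumes at both scans and label it supportive, since that restriction depends on the year-2 result.

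The cost is wording only if the analysis has not been run. The Background of SAP version 1.1 says that the document was prepared for release with publication of the data, so results may exist. In that case, report both populations and say which was primary. No new data are needed.
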